10.5 STATISTICAL ANALYSIS METHODOLOGY

The primary safety and performance endpoints will be summarized by counts, percentages and corresponding 95% confidence intervals. Other categorical variables will be summarized by counts and percentages. Continuous variables will be summarized using means, medians, ranges and standard deviations. Time to event analysis, including survival probabilities and standard errors, will be estimated using the Kaplan Meier method. Time to event will be calculated in days and standard errors will use the greenwood algorithm.

Statistical calculations will be based on all available data. No missing value imputations are planned for the primary and secondary analyses will be performed. Missing month and days for adverse events will be imputed. Regarding the secondary endpoint, an initial analysis of apparent product failure will be conducted once 50 subjects achieve 12 months of follow-up. Thereafter, a failure analysis will be repeated for each subsequent 10 subjects achieving 12 months of follow-up. The rates of apparent product failure will be deemed unacceptable if the lower limit of any 95% confidence interval at 12 months is above 6%.

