9.8.2 SURGICAL VALVE INTERVENTION

In the event of explant/subject surgical valve intervention, every effort should be made to obtain a copy of the procedure notes as well as any accompanying imaging data (CT, echo). Information on the cause of explant/surgical intervention will be determined by the investigator(s) and reported in the study EDC system. Subjects who have a surgical reintervention or whose device is explanted will be followed for 30 days or until resolution of any adverse events related to the procedure, and then exited from the study. Effort should also be made to return any explanted study devices to the Sponsor for analysis by the Edwards Complaint Handling team. Return kits for explanted devices will be provided, upon request, by the Edwards Surgical Complaint Handling Department.

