10.4 ADDITIONAL PLANNED ANALYSES

The following analyses are planned:

- Technical success defined as survival and exit from the operating room (OR) with successful implantation of 3 or more ePTFE chords
- Freedom from major device or procedure-related serious adverse event (SAE) at 30 days, 1 year and 2 years post-implant
- Quality of Life (change from baseline to 1 and 6 months)
- 6 minute walk test (change from baseline to 1 and 6 months)
- Freedom from ePTFE chord rupture as reported by echo core lab at 1 year and 2 years post-implant
- Freedom from reoperation or re-intervention due to ePTFE chord rupture at 1 year and 2 years post-implant
- Functional improvement from baseline NYHA Functional Classification at 1 year and 2 years post-implant
- Freedom from reoperation or reintervention on the mitral valve annually through 5 years post-implant
- Freedom from \geq moderate MR annually through 5 years post-implant

To address the uncertainty around ePTFE chord rupture, an initial analysis of apparent product failure will be conducted once 50 patients achieve 12 months of follow-up. Thereafter, a failure analysis will be repeated for each subsequent 10 patients achieving 12 months of follow-up. The rates of apparent product failure will be deemed unacceptable if the lower limit of any 95% confidence interval at 12 months is above 6% (inclusive of 95% CI). It should be noted that “Failure” is defined conservatively as suspected ePTFE chord rupture based only on echo. Confirmation of a rupture, which requires reoperation, is not required.

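### Section 10.5 names only Kaplan-Meier and leaves the handling of death unstated; if deaths are censored, 5-year mitral reoperation risk is overstated by about 2 points at the protocol's prior rates

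*Combined protocol and SAP*

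**What the plan says.** Section 10.5 states: "Time to event analysis, including survival probabilities and standard errors, will be estimated using the Kaplan Meier method". It adds that "standard errors will use the greenwood algorithm". No other time-to-event estimator is named. The section does not list the endpoints to which Kaplan-Meier applies, and it does not say whether death is a censoring event or a competing one. The same paragraph provides that "Other categorical variables will be summarized by counts and percentages".

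Three endpoints in Section 10.4 are affected:

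- "Freedom from reoperation or reintervention on the mitral valve annually through 5 years post-implant"
- "Freedom from reoperation or re-intervention due to ePTFE chord rupture at 1 year and 2 years post-implant"
- "Freedom from ePTFE chord rupture as reported by echo core lab at 1 year and 2 years post-implant"

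Only the first of these runs to 5 years.

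Death is an exit reason in Section 9.7. On reoperation, Section 9.8.2 says: "Subjects who have a surgical reintervention or whose device is explanted will be followed for 30 days", or until related adverse events resolve, and that they then leave the study. Section 9.7 words this exit differently: it covers surgical reinterventions in which the device is explanted.

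**The concern.** A patient who has died can no longer be reoperated. Kaplan-Meier with deaths censored treats that patient as still at risk, with the same hazard as the survivors. One minus Kaplan-Meier then describes reoperation in a setting where nobody dies first. It does not describe the share of treated patients who are reoperated, and it cannot fall below that share.

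The stated objective (Section 7.1) is long-term safety and performance, and Section 8.1 sets no upper age limit. The 5-year reoperation figure is therefore likely to be read as a patient's risk. The plan should say which quantity it reports.

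For the rupture endpoints a second event can compete. A reoperation for another cause may end follow-up before any rupture is seen.

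**Working it through.** **Inputs (Section 6.3.4, Table 1), reproduced first.** Late reoperation is 10/99.0 = 10.1 per 100 patient-years and late death is 2/99.0 = 2.0. Early (to day 30) reoperation and early death are each 1/62 = 1.6%. The plan gives no Kaplan-Meier or cumulative-incidence figure to reproduce. Its precision goal of 5% or better for rates of 2% to 17% (Section 10.2.1) does reproduce at n = 250: 1.96 × √(0.17 × 0.83/250) = 4.7 points, and 1.7 points at 2%.

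Let h be the reoperation hazard and d the death hazard, both constant and independent.

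**Step 1: late rates only, 5 years.**

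- One minus Kaplan-Meier: 1 − exp(−5h) = 1 − exp(−0.505) = 39.6%.
- Cumulative incidence: h/(h+d) × [1 − exp(−5(h+d))] = (0.101/0.121) × [1 − exp(−0.605)] = 0.8347 × 0.4539 = 37.9%. A simulation of 200,000 patients gave 38.0%.
- The gap is about 1.8 points (1.7 from the rounded figures).

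**Step 2: add the 30-day events.** The remaining time is T = 5 − 30/365.25 = 4.918 years.

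- One minus Kaplan-Meier: 1 − (61/62) × exp(−0.101 × 4.918) = 1 − 0.9839 × 0.6085 = 40.1%.
- Cumulative incidence: 1/62 + (60/62) × 0.8347 × [1 − exp(−0.121 × 4.918)] = 0.0161 + 0.9677 × 0.8347 × 0.4485 = 37.8%.
- The gap is 2.3 points. In 250 patients that is 0.023 × 250, or about 6 patients.
- The same formulas give 10.3% against 10.1% at 1 year and 18.9% against 18.3% at 2 years.

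**Step 3: vary the rates (30-day events kept).** Every row except the second uses at least one assumed rate.

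| Reoperation per 100 pt-yr | Death per 100 pt-yr | 1 − KM at 5 y | Cumulative incidence | Gap (points) |
|---|---|---|---|---|
| 10.1 | 1 | 40.1% | 38.7% | 1.4 |
| 10.1 | 2 | 40.1% | 37.8% | 2.3 |
| 10.1 | 4 | 40.1% | 36.3% | 3.8 |
| 10.1 | 8 | 40.1% | 33.4% | 6.7 |
| 5 | 2 | 23.1% | 21.7% | 1.4 |
| 2 | 2 | 10.8% | 10.3% | 0.5 |

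**Step 4: rupture-related reoperation.** The documents do not give the share s of reoperations due to rupture, so I assume 25%, 50% and 75%. The event hazard is 0.101s and the competing hazard is 0.020 + 0.101(1 − s). The early masses are s/62 and (2 − s)/62. Every other-cause reoperation is taken to end follow-up.

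| s | 1 y: 1 − KM vs cumulative incidence | 2 y: 1 − KM vs cumulative incidence |
|---|---|---|
| 25% | 2.7% vs 2.5% | 5.1% vs 4.6% |
| 50% | 5.3% vs 5.1% | 10.0% vs 9.2% |
| 75% | 7.8% vs 7.6% | 14.6% vs 13.8% |

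The gap stays under 1 point throughout.

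**Step 5: compare with sampling error.** At n = 250 without dropout, the 95% half-width near 39% is 1.96 × √(0.39 × 0.61/250) = 6.0 points.

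**The case against.** The other side has several good arguments.

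- **Censoring at death is not written.** Section 10.5 does not state it, nor that these endpoints use Kaplan-Meier. Section 10.6.4 refers to a pre-specified SAP, and any fuller text is not in the document reviewed. This stands: the defect is an unstated rule, not a wrong one. A reader might infer that the plan instructs censoring at death, but the text does not say so.
- **Kaplan-Meier freedom from reoperation is a legitimate device-durability measure.** This stands, and is why it should be kept. The error lies only in reading its complement as the share of patients reoperated, and the plan does not guard against that reading.
- **Counts and percentages may be reported as well.** This stands in part. Crude percentages do not estimate 5-year risk properly once follow-up is incomplete.
- **The gap is small.** At the prior rates it is about 2 points against a half-width of 6. These are descriptive analyses without a hypothesis test. Sections 6.3.6.1 and 13.2.1 describe changes meant to reduce ruptures, which would shrink the gap. All of this stands and keeps the point minor. Even so, the gap is systematic, and a larger sample would not remove it.

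Two further readings are tempting. One is that chord-rupture risk is overstated out to 5 years; both rupture endpoints stop at 2 years. The other is that other-cause reoperation competes with mitral reoperation; for that endpoint any mitral reoperation is itself the event.

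**Conclusion.** The point holds as a minor one. Section 10.5 leaves the handling of death open. Under the usual default, 5-year mitral reoperation would be overstated as a patient-level risk by about 2 points at the protocol's own rates. The gap is about 0.5 points if reoperation falls to 2 per 100 patient-years, and 1.4 to 6.7 points if mortality lies between 1 and 8 per 100 patient-years. For rupture-related reoperation at 1 and 2 years it is under 1 point.

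These figures assume constant, independent hazards after day 30 and rates from 62 prior implants with only two late deaths. They also take the study-device reoperations of Table 1 to stand for mitral reoperation or reintervention. The documents give no rate for echo-reported rupture, so Step 4 serves only as a guide for that endpoint.

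A reader might infer a gap of 4 points or more as the expected result. That needs mortality well above the 2.0 per 100 patient-years in Table 1. The absence of an upper age limit makes higher mortality possible but does not document it. The 5-year survival that Section 6.1 quotes for patients over 80 concerns a different group.

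It is also not settled that every other-cause reoperation ends follow-up, because Sections 9.7 and 9.8.2 word the exit differently. Neither requires exit after a non-surgical reintervention.

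**What to change.** In Section 10.5:

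1. For freedom from mitral reoperation or reintervention through 5 years, add the Aalen-Johansen cumulative incidence with 95% confidence intervals, with death as the competing event. Quote it as the patient-level risk.
2. Keep the Kaplan-Meier estimate, labelled as durability in the absence of death.
3. For chord rupture and rupture-related reoperation at 1 and 2 years, name death and any other-cause reoperation that ends follow-up as competing events.

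Reconcile the exit wording in Sections 9.7 and 9.8.2, so that it is clear which reoperations end observation.

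The cost is a few sentences and a few lines of code. Sections 9.8.1 and 9.8.2 already provide for recording deaths and surgical reinterventions, so no new data are needed. The drawback is two figures per endpoint to explain; keeping Kaplan-Meier preserves comparison with earlier device reports.

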10.6 METHODS USED TO MINIMISE BIAS

The following methods are employed to minimise bias in the study:

10.6.1 INCLUSION BIAS

All patients clinically eligible for treatment with the HARPOON System device and who meet the study criteria will be offered inclusion in the study.

10.6.2 ENDPOINT EVALUATION

An independent Echo Core Lab will evaluate all echocardiograms performed as part of the protocol (and in particular in relationship to the Primary Performance Endpoint and the Secondary chord rupture monitoring endpoint), and an independent Clinical Events Committee will adjudicate all potential safety endpoints and reinterventions through 2-year follow-up.

10.6.3 REPORTED DATA VERACITY

Routine monitoring will be conducted for all reported data according to the study monitoring plan.

10.6.4 AVOIDING ANALYSIS BIAS

Statistical analysis will be conducted according to a pre-specified Statistical Analysis Plan (SAP).

10.6.5 PUBLICATION BIAS

The study will be registered at clinicaltrials.gov to ensure that publication of results will occur whether results are favourable or unfavourable to the sponsor.

11.0 SAFETY REPORTING

Subjects will be carefully monitored during the study for possible Adverse Events (AEs) from the time of the subject's enrolment to the completion of their participation in the study.

11.1 DEFINITIONS OF ADVERSE EVENTS AND DEVICE DEFICIENCIES

All adverse events will be fully investigated by the Investigator and classified in line with the definition of the ISO 14155:2011 below (Table 4).

Table 4: Adverse Event Definitions

Term	Definition
Adverse event (AE)	
Any untoward medical occurrence, unintended disease or injury, or untoward clinical signs (including abnormal laboratory findings) in subjects, users or other persons, whether or not related to the investigational medical device
 
NOTE 1: This definition includes events related to the investigational medical device or the comparator.
 
NOTE 2: This definition includes events related to the procedures involved.
 
NOTE 3: For users or other persons, this definition is restricted to events related to investigational medical devices.

Serious adverse event (SAE)	
An adverse event that (ISO 14155):
 
• led to a death,• led to serious deterioration in the health of the subject, that either resulted in
• a life-threatening illness or injury, or• a permanent impairment of a body structure or a body function, or• in-subject or prolonged hospitalization, or• medical or surgical intervention to prevent life-threatening illness or injury or permanent impairment to a body structure or a body function,• led to fetal distress, fetal death or a congenital abnormality or birth defect 
NOTE: Planned hospitalization for a pre-existing condition, or a procedure required by the CIP, without serious deterioration in health, is not considered a serious adverse event.

Device deficiency	Inadequacy of an investigational medical device related to its identity, quality, durability, reliability, safety or performance. This may include malfunctions, use error, or inadequacy in the information supplied by the manufacturer.
Device malfunction	Failure of an investigational medical device to perform in accordance

Term	Definition
	with its intended purpose when used in accordance with the instructions or use or CIP.
Adverse device effect (ADE)	
Adverse event related to the use of an investigational medical device
 
NOTE 1: This definition includes adverse events resulting from insufficient or inadequate instructions for use, deployment, implantation, installation, or operation, or any malfunction of the investigational medical device.
 
NOTE 2: This definition includes any event resulting from use error or from intentional misuse of the investigational medical device

Serious adverse device effect (SADE)	Adverse device effect that has resulted in any of the consequences characteristic of a serious adverse event.
Unanticipated Serious Adverse Device Effect (USADE)	
Serious adverse device effect which by its nature, incidence, severity or outcome has not been identified in the current version of the risk analysis report.
 
NOTE: Anticipated serious adverse device effect (ASADE) is an effect which by its nature, incidence, severity or outcome has been identified in the risk analysis report.

Use Error	
Act or omission of an act that results in a different medical device response than intended by the manufacturer or expected by the user
 
NOTE 1: Use error includes slips, lapses, and mistakes.
 
NOTE 2: An unexpected physiological response of the subject does not in itself constitute a use error.

11.2 CAUSALITY RELATIONSHIP

Relatedness of the AE to the index procedure or the HARPOON System device itself will be evaluated by the investigator.

The causal relationship of the AE to the device and the procedure will be rated as follows:

1) **Not related:** relationship to the device or procedures can be excluded when:

- the event is not a known side effect of the product category the device belongs to or of similar devices and procedures;
- the event has no temporal relationship with the use of the investigational device or the procedures;

- the serious event does not follow a known response pattern to the medical device (if the response pattern is previously known) and is biologically implausible;
- the discontinuation of medical device application or the reduction of the level of activation/exposure - when clinically feasible – and reintroduction of its use (or increase of the level of activation/exposure), do not impact on the serious event;
- the event involves a body-site or an organ not expected to be affected by the device or procedure;
- the serious event can be attributed to another cause (e.g. an underlying or concurrent illness/ clinical condition, an effect of another device, drug, treatment or other risk factors);
- harms to the subject are not clearly due to use error;
- In order to establish the non-relatedness, not all the criteria listed above might be met at the same time, depending on the type of device/procedures and the serious event.

2) **Unlikely:** the relationship with the use of the device seems not relevant and/or the event can be reasonably explained by another cause, but additional information may be obtained.

3) **Possible:** the relationship with the use of the investigational device is weak but cannot be ruled out completely. Alternative causes are also possible (e.g. an underlying or concurrent illness/ clinical condition or/and an effect of another device, drug or treatment). Cases where relatedness cannot be assessed or no information has been obtained should also be classified as possible.

4) **Probable:** the relationship with the use of the investigational device seems relevant and/or the event cannot reasonably have been explained by another cause, but additional information may be obtained.

5) **Causal relationship:** the serious event is associated with the investigational device or with procedures beyond reasonable doubt when:

- the event is a known side effect of the product category the device belongs to or of similar devices and procedures;
- the event has a temporal relationship with investigational device use/application or procedures;
- the event involves a body-site or organ that
- the investigational device or procedures are applied to;
- the investigational device or procedures have an effect on;
- the serious event follows a known response pattern to the medical device (if the response pattern is previously known);
- the discontinuation of medical device application (or reduction of the level of activation/exposure) and reintroduction of its use (or increase of the level of activation/exposure), impact on the serious event (when clinically feasible);

- other possible causes (e.g. an underlying or concurrent illness/ clinical condition or/and an effect of another device, drug or treatment) have been adequately ruled out;
- harm to the subject is due to error in use.

In order to establish the relatedness, not all the criteria listed above might be met at the same time, depending on the type of device/procedures and the serious event.

11.3 REPORTING ADVERSE EVENTS

11.3.1 REPORTING BY THE INVESTIGATOR

Adverse Event reporting to the sponsor is the Investigator's responsibility and will start at time of enrolment and will continue until a closure of the study follow-up or until a subject exits the study.

Adverse events will be recorded on the Electronic Case Report Form by the Clinical Study Coordinator (or any designated site personnel). If the system is not accessible, the event can be reported to sponsor by using the following e-mail address: [contact]

AE information (start and stop date, description of event, severity, and relatedness to the HARPOON System procedure and the HARPOON System) will be assessed and **recorded** in the EDC system **in a timely manner** by the site. Whether an AE meets the definition for serious adverse event will be determined by the study investigator using the ISO 14155 definition (see **Table 4**). Relatedness of the AE to the index procedure or the HARPOON System device itself will be judged by the investigator by using the causality categories listed in Section 11.2.

The investigator shall notify the sponsor immediately and **not later than 3 calendar days** after the investigator has become aware of a SAE or device deficiency that might have led to a SAE by completing the Adverse Event electronic Case Report Form.

All reported events will be followed until resolution, stabilization or 30 days after the last subject implanted has completed the study, whichever occurs first.

11.3.2 SAFETY ASSESSMENT AND REPORTING BY THE SPONSOR

The Safety Overview and Process (Adverse Event Handling) in the ASCEND Study has been established as an independent two-level review of reported Adverse Events (AE) and Device Deficiencies conducted by the Sponsor's Safety Department and an independent clinical adjudication of potential safety endpoints (Death, stroke, bleeding) and reintervention post index procedure by the Clinical Events Committee (CEC). The process includes:

Adverse Event Review Upon receipt of Adverse Event (AE) notification (electronic EDC, email [contact]), reported by the Investigator and/or Research Coordinator, Safety conducts a Sponsor Assessment of each AE on the AE Review form as per Regulatory requirements specific to the

study/region where the study is conducted, per MEDDEV 2.7/3 (Clinical Investigations: Serious Adverse Event Reporting), MEDDEV 2.12-1 rev 8 (Vigilance Reporting), ISO 14155-2011 (Clinical investigation of Medical Devices for Human Subjects) where applicable and internal EW standard operating procedures, including USADE decision and complaint reporting.

AEs are assessed as serious or non-serious, assessed for causality, and if anticipated or unanticipated. Any updated AE is re-assessed for seriousness, causality and if anticipated or unanticipated. In any urgent situation concerning patient's safety or to report an unanticipated adverse device effect (USADE), the sites can contact Edwards Surgical Safety, Safety Officer directly.

- **USADE Reporting** During Safety's AE review, any AE assessed as a USADE will be reported as soon as possible to EW Regulatory Affairs (RA) and by RA to the EU Regulatory Authorities within local regulatory requirements and timelines. Safety will notify all ethics committees and Investigators as required.
- **CRO Responsibilities** This study is monitored by an external CRO to ensure complete AEs and SAEs reporting through a monitoring process as identified/described in the monitoring plan, and to verify that all reported data are consistent and queries answered.
- **Complaint Reporting** In addition, as required in post market investigation, each AE will be assessed in regards to a device causality, and will be reported to the Edwards EU Complaint Handling group. EU Complaint Group will assess and report appropriately all device complaints to EU Authorities as per MEDDEV 2.12-1.

Clinical Events Committee (CEC) Adjudication During the Sponsor's Safety review potential safety endpoints and reinterventions are identified for adjudication. If an event meets the safety endpoint definition as specified in the protocol and CEC Charter (or can possibly be related to any safety endpoint, although reported as "Other"), the source documents are requested from the site to support CEC adjudication.

The CEC reviews forwarded events and their source documents to verify if additional records are required, and to determine if the event meets the safety endpoint definition (as in the CEC Charter). During this process non-reported events can be identified by the CEC and queried to Edwards Safety Team for additional information. CEC activities are outlined in the CEC Charter.

